2.2 Secondary Objective

Contrast effects of walking with optical flow perturbations to those of normal treadmill walking.

3 INVESTIGATIONAL PLAN (brief overview)

3.1 Study Design

(Session A: Normal walking, Session B: Continuous optical flow perturbations). In a randomized cross-over designed (assigned at enrollment using a random number generator), subjects will walk normally (session A) and be exposed to continuous side-to-side motions of the virtual hallway (Session B). These walking trials will last up to 20 min and will be separated by at least one week.

3.2 Study Duration, Enrollment and Number of Subjects

This study will last up to 36 months. Subject recruitment and data collection will take up to 24 months. The remaining 12 months will focus on data analysis, data interpretation, and manuscript preparation. We will recruit up to 20 older adults to participate.

3.3 Study Population

Inclusion Criteria:

1. Subjects Age 65+ years
2. Be able to walk without an assistive aid (i.e., walker, cane)
3. Have the full capacity to provide informed consent

Exclusion Criteria:

1. Current lower extremity injury or fracture
2. Taking medication that causes dizziness
3. Have a leg prosthesis
4. Prisoners
5. Individuals lacking the capacity to provide informed consent

4 STUDY PROCEDURES (what will be done)

Subjects will be comfortably fit with a safety harness and instructed on all safety procedures. Subjects will then walk at their preferred speed on a force-sensing treadmill for 5 min to acclimate to the equipment and allow their movement patterns to stabilize.

Subjects will then complete a block protocol design with pre and post measurements separated by up to 20 min of normal treadmill walking (Session A) or in the presence of optical flow perturbations (Session B). Pre and post measurements will include baseline measurements during normal walking and:

- 1) Foot placement targeting task. Subjects will be exposed to a series of footprint targets intermittently projected onto the treadmill belt. Subjects will be asked to direct their feet to the target with their next step as accurately as possible.
- 2) Auditory 'Stroop' task. While wearing headphones with a microphone, subjects will hear the words high and low in pitches that are either high or low and asked to verbally identify the pitch of those words as quickly as possible.

Subject Completion/ Withdrawal procedures

If subjects are unable to complete the protocol or suffer a musculoskeletal injury before or during the time period when they are involved in the study, they will be withdrawn from the study.

5 STUDY EVALUATIONS AND MEASUREMENTS (how measurements will be made)

3D motion capture and an instrumented treadmill will record the position and orientation of body segments and joints and ground reaction forces. Using custom software, we will compute the mean and standard deviation of step width variability, postural sway variability, and margin of stability variability. The outcome measure from the foot placement targeting task will be foot placement accuracy. The outcome measures from the auditory Stroop task will be cognitive-motor interference accuracy and response time. Efficacy measurements will be made using the change in each outcome measure after walking normally or with optical flow perturbations.

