1.3 Relevant Literature and Data

The investigators have a significant history of testing the effects of optical flow perturbations on walking balance in young and older adults and in patients with multiple sclerosis. Our cumulative evidence from these studies (listed below) demonstrate that older adults are significantly more susceptible to these perturbations than young

adults (Fig. 1). Accordingly, we now know that this environment uniquely disrupts walking balance in older adults, thereby providing an opportunity to “practice” corrective motor adjustments relevant to preserving balance.

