6.1 Statistical Methods

A two-way rmANOVA will test for significant main effects and interactions between time (Pre versus Post) and experimental session (perturbations versus normal walking). Significance will be defined for each main effect using an alpha level of 0.05.

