8 SAFETY MANAGEMENT

If a subject needs immediate medical assistance, we will call “911” for emergency services. Should a subject need non-urgent medical or psychological follow-up, research members will contact UNC Health Care to provide referrals.

At least one research staff member will be monitoring the subjects' movement patterns during the data collection. If the subject experiences any discomfort, the data collection will be stopped immediately.

If any member of the research team encounters unanticipated problems (including but not limited to adverse events), we will make necessary adjustments to the protocol and, where appropriate, report these events to IRB personnel. Our goal with protocol adjustments will be to further lessen the likelihood of unanticipated problems.

If subjects are unable to complete the protocol or suffer a musculoskeletal injury before or during the time period when they are involved in the study, they will be withdrawn from the study.

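### The Section 6.1 repeated-measures ANOVA drops anyone with an unfinished session, so the result loses precision and describes only those who complete both sessions

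*Combined protocol and SAP*

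**What the plan says.** Four parts of the document bear on this.

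- **Stopping.** Section 8, and the synopsis in the same words: "If the subject experiences any discomfort, the data collection will be stopped immediately". The rule covers both sessions. Resuming or repeating a session is not mentioned.
- **Withdrawal.** Section 4, repeated in Section 8: "If subjects are unable to complete the protocol or suffer a musculoskeletal injury before or during the time period" of their involvement, "they will be withdrawn from the study". What happens to data already recorded is not stated.
- **Exposure and outcome.** Section 3.1: "These walking trials will last up to 20 min and will be separated by at least one week". No minimum is set for a session to count as completed. Sections 4 and 5 define efficacy as the change from before to after the walking block, so a session without its Post block yields no outcome.
- **Analysis.** Section 6.1: "A two-way rmANOVA will test for significant main effects and interactions between time (Pre versus Post) and experimental session". The synopsis instead describes a one-way analysis over time for each session. Neither place gives an analysis set, a missing-data rule or a plan to report stops.

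**The concern.** A repeated-measures ANOVA of time by session, run in its standard form, uses only subjects with all four cells: Pre and Post in Session A, and Pre and Post in Session B. A subject whose second session is stopped before the Post block therefore leaves the analysis, and the completed first session goes too. A subject withdrawn during the first session never reaches the second.

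Two things are at stake. Usable data go unused in a study capped at 20 subjects. And the result then describes those who got through both sessions, while the objectives in Section 2 speak of older adults in general. How many could not finish is also of interest in a proof of concept for a training method, and the plan does not commit to reporting it.

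**Working it through.** **1. The plan's own figure.** Section 6 gives n = 14 per group for 90% power, comparing older (1.38 ± 0.20) with young (1.20 ± 0.10) adults. The pooled SD is √((0.20² + 0.10²)/2) = 0.158, and 0.18/0.158 = 1.14. By t-test, n = 14 gives power 0.901 one-sided and 0.826 two-sided, so the figure reproduces only one-sided. It has no dropout term and concerns a different comparison, so it neither supports nor weakens this point. If 14 completers are wanted, the cap of 20 allows a loss of 6/20 = 30%.

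**2. Which cells a stopped subject supplies.**

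| Event | Cells recorded | Used by the 6.1 ANOVA |
|---|---|---|
| A completed first, B stopped before Post | A Pre, A Post, B Pre | none |
| B first, stopped before Post, then withdrawn | B Pre | none |
| B completed first, A missed | B Pre, B Post | none |

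The third subject provides the perturbed-session change named in the primary objective (Section 2.1) and is still left out.

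**3. Precision.** Assume 4 of 20 subjects stop and a random-intercept model with residual variance σ². The interaction is (B Post − B Pre) − (A Post − A Pre), with variance 4σ² per completer.

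- All 20 complete: 4σ²/20 = 0.200σ².
- Completers only: 4σ²/16 = 0.250σ². The standard error is √(0.250/0.200) = 1.12 times that with 20.
- Completers, plus four subjects with Session A only: 2σ²/20 + 2σ²/16 = 0.225σ², which is 10% below completers only.

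Other patterns need generalised least squares. The variance is c′(ΣXᵢ′Vᵢ⁻¹Xᵢ)⁻¹c, where c is the interaction contrast on the four cell means and Vᵢ is the random-intercept covariance of the recorded cells. With intraclass correlation from 0.3 to 0.9:

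- four subjects with A Pre, A Post and B Pre: 13 to 14% below completers only;
- two such subjects and two with B Pre only: 8 to 9% below.

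The gain is therefore about 8 to 14%. For scale, the standardized paired effect detectable with 90% power (two-sided 0.05) is 0.76 with 20 completers, 0.87 with 16 and 0.94 with 14.

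**4. Applicability.** The documents give no rate of stopping and no link between susceptibility and response, so this step is illustration only. If the most susceptible fraction q is lost, and susceptibility correlates ρ with the change, the completers' mean change differs from that of all enrolled by ρφ(z)/(1 − q) SD, with z the 1 − q normal quantile.

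| q | φ(z)/(1 − q) | ρ = 0 | ρ = 0.3 | ρ = 0.5 | ρ = 0.7 |
|---|---|---|---|---|---|
| 10% | 0.1755/0.9 = 0.195 | 0 | 0.058 | 0.097 | 0.136 |
| 20% | 0.2800/0.8 = 0.350 | 0 | 0.105 | 0.175 | 0.245 |
| 30% | 0.3477/0.7 = 0.497 | 0 | 0.149 | 0.248 | 0.348 |

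The standard error of a mean change is 1/√18 = 0.24 SD with 18 completers and 1/√16 = 0.25 SD with 16. At 10 to 20% loss the shift is at most about one standard error. The sign of ρ is unknown, and the shift is nil if nobody stops.

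**The case against.** A reader might infer something stronger: that these rules remove the people most disturbed by the perturbation and so bias the comparison of Session B with Session A. The case against that is good, and most of it stands.

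- **The comparison is within subject.** Anyone dropped leaves both sessions, so completers remain balanced and their contrast is valid for them. This stands.
- **More stops in Session B is an inference.** Section 1.3 says "this environment uniquely disrupts walking balance in older adults", which concerns balance, not discomfort or stopping. The stop rule covers both sessions, and the true number of stops could be zero. This stands.
- **A stop need not mean withdrawal.** The walking time is an upper limit with no minimum, so a shortened block followed by the Post measurement might count as complete. This stands, and it limits the point to sessions that end without a Post block or are missed.
- **Nothing says data are discarded.** True. The loss comes from the form of the analysis, not from a rule to delete data.
- **The synopsis analysis runs per session** and would keep a completed session. True, but it cannot supply the contrast between sessions that Section 2.2 asks for.
- **A mixed model would not cure selection on susceptibility.** Pre values come from normal walking, and Section 1.2 says age-related differences were not apparent there, so they may carry little information on who is susceptible. This stands, and is why the case for the model is precision only.

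**Conclusion.** The point holds as one of precision and applicability. As written, the Section 6.1 analysis in its standard form would leave out any subject with an unfinished or missed session, and the result would describe those who complete both. With 4 of 20 stopping under a random-intercept model, keeping all recorded data lowers the variance of the interaction by about 8 to 14%; with no stops there is no gain. How far completers differ from the enrolled group cannot be sized from the documents: the illustrative range is 0 to 0.35 SD for losses up to 30% and correlations up to 0.7, in an unknown direction.

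The documents do not support saying that the contrast between sessions is biased among those analysed, that stops will concentrate in Session B, or that the analysed subjects must have tolerated a full 20 minutes. The stopping and withdrawal rules themselves are not in question.

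**What to change.** Leave the discomfort, injury and withdrawal rules as they are. Then:

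- **Section 6.1:** replace the repeated-measures ANOVA with a linear mixed model with time, session and their interaction as fixed effects, a random subject effect, and small-sample degrees of freedom. State that it uses all recorded data, including those of subjects later withdrawn. With complete data it returns the same estimated interaction as the ANOVA.
- **Reporting:** commit in advance to giving the number and minute of stops by session and by sequence. If stops are more frequent in Session B, limit the conclusion to those who completed it.

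The cost is wording in Section 6.1, a field for the time of any stop, and slightly more analysis work. No added subjects or procedures are needed. The model assumes data missing at random. It gains precision but does not remove selection on susceptibility to the perturbation, and similar Pre values in completers and non-completers should not be read as evidence that such selection is absent.

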6 STATISTICAL CONSIDERATION

Sample size is based on our published estimates of age-related differences in balance outcome measures. n=14 subjects per group would have 90% power to detect ($p<0.05$) a difference in dynamic instability during visually perturbed walking between healthy older (1.38 ± 0.20 , unitless) and healthy young (1.20 ± 0.10 , unitless) adults (Franz et al., 2015). This number of subjects would also sufficiently power our detecting differences in step width variability (8.92 ± 1.00 vs. 4.02 ± 0.96) (Francis et al., 2015).

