Study Rationale	
One third of adults age 65 and older fall annually with 20-30% of falls resulting in serious injuries. In 2009 alone, falls in older adults resulted in nearly 2.2 million emergency room visits. In 2000, direct medical cost of non-fatal falls in adults over age 65 was \$19 billion, and in 2007 that cost was projected to increase to \$54.9 billion/year by 2020. However, despite considerable efforts, falls rates over this time have been highly resistant to change. Thus, there is a critical need for more effective diagnostic efforts to identify older adults at risk of falls and rehabilitative efforts to successfully mitigate that risk once identified. Consistent with studies on the postural control of standing, our recent findings suggest that older adults prioritize visual feedback to control balance in walking.
 
Accordingly, older adults are more susceptible than young adults to optical flow perturbations applied in the safety of virtual reality (VR). These perturbations elicit the visual perception of walking instability, and provide the opportunity to practice walking balance corrections in a controlled environment. The purpose of this proof of concept study is to investigate the propensity for time-dependent tuning of walking balance control and the presence of aftereffects in older adults following a single session of optical flow perturbation training.

Study Objective(s)	To investigate the propensity for time-dependent tuning of walking balance control and the presence of aftereffects in older adults following a single session of optical flow perturbation training.
Test Article(s) (If Applicable)	Mediolateral (ML; i.e., side-to-side) optical flow perturbations applied during treadmill walking using a projection-based virtual reality system.
Study Design	A randomized, crossover design that included a control session of normal unperturbed walking and an experimental session that incorporated mediolateral optical flow perturbations during walking.
Subject Population	Inclusion Criteria
key criteria for Inclusion and Exclusion:	
 1. Subjects Age 65+ years 2. Be able to walk without an assistive aid (i.e., walker, cane) 3. Have the full capacity to provide informed consent
	Exclusion Criteria

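### The 90% power in Section 6 is for an older-versus-young comparison that this trial does not make

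*Combined protocol and SAP*

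**What the plan says.** Section 6 explains where the number comes from: "Sample size is based on our published estimates of age-related differences in balance outcome measures". It then says that "n=14 subjects per group would have 90% power to detect" "a difference in dynamic instability during visually perturbed walking between healthy older" adults (1.38 ± 0.20) and healthy young adults (1.20 ± 0.10), at p<0.05 with sidedness not stated. It adds: "This number of subjects would also sufficiently power our detecting differences in step width variability", citing 8.92 ± 1.00 vs. 4.02 ± 0.96 without labelling the two sets of values or giving a power percentage.

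The rest of the document describes a different comparison:

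- **Population.** The age criterion in Section 3.3 is "Subjects Age 65+ years", and Section 3.2 caps enrolment at 20 older adults.
- **Design.** The synopsis describes "A randomized, crossover design that included a control session of normal unperturbed walking" and an experimental session with perturbations. Each subject does both.
- **Efficacy measure.** Section 5 says: "Efficacy measurements will be made using the change in each outcome measure after walking normally or with optical flow perturbations".
- **Tests.** The synopsis plans a one-way repeated-measures ANOVA for time. Section 6.1 plans a two-way repeated-measures ANOVA for time (Pre, Post), session and their interaction.

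**The concern.** A power statement should describe the test that the trial will run. Here the contrast is between age groups, while the trial contrasts Pre with Post, and one session with the other, in the same people. A difference between age groups is not a training effect, and a between-person SD is not an SD of change, so the figure does not carry over.

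The 90% is the only numeric power in the plan, so a reader is likely to take it as the trial's power. A null result could then be read as good evidence that one training session has no effect, although the plan never says what pre-post change, or what between-session difference in change, the enrolled number could detect.

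**Working it through.** **1. Reproduce the stated figure.** Inputs from Section 6: means 1.38 and 1.20, ± values 0.20 and 0.10, 14 per group, alpha 0.05. Reading ± as SD is an assumption.

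- Difference = 1.38 − 1.20 = 0.18
- Pooled SD = √((0.20² + 0.10²)/2) = 0.158
- d = 0.18/0.158 = 1.14
- Two-sample t-test, 26 df: power 90.1% one-sided, 82.6% two-sided

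The stated 90% therefore reproduces as a one-sided comparison of two independent groups. Using the simple average SD of 0.15 instead, two-sided power is 86.3%.

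For step width variability, the pooled SD is √((1.00² + 0.96²)/2) = 0.98 and the difference is 4.90, about 5 SDs. Treated as two independent groups, power is essentially 100%.

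**2. Compare it with the planned tests.**

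| | Section 6 power | Synopsis test | Section 6.1 tests |
|---|---|---|---|
| Contrast | older vs young | time | time, session, time × session |
| Groups | two, independent | one, each subject measured repeatedly | one, each subject measured repeatedly |
| Outcome | dynamic instability | the study's dependent variables | outcomes not named |
| SD needed | between-person | SD of change | SD of each within-subject contrast |

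Dynamic instability is not a listed outcome under that name. Step width variability is a primary outcome. Section 6's opening sentence makes its two values an age difference on the natural reading. If they are instead two walking conditions, they are still levels, with no SD of change and no expected pre-post change.

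**3. What the enrolled number can detect.** For one within-subject contrast (1 df), power follows from the noncentral t with n − 1 df and noncentrality δ√n, where δ is the mean difference divided by the SD of that difference. Solving for δ at two-sided 0.05:

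| Completers | 90% power | 80% power |
|---|---|---|
| 12 | 1.03 | 0.89 |
| 14 | 0.94 | 0.81 |
| 16 | 0.87 | 0.75 |
| 18 | 0.81 | 0.70 |
| 20 | 0.76 | 0.66 |

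Simulation with 400,000 runs agreed: 90.0% at δ = 0.938 with 14, and 90.0% at δ = 0.764 with 20. The completer numbers are assumptions, because the plan gives only a ceiling and Section 4 withdraws subjects: "If subjects are unable to complete the protocol or suffer a musculoskeletal injury".

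**4. Each contrast has its own SD.** Assume equal SDs of change in the two sessions and a correlation r between a subject's two changes. Then SD(between-session difference in change) / SD(one session's change) = √(2(1 − r)). This is 1.61 at r = −0.3, 1.41 at 0, 1.18 at 0.3, 1.00 at 0.5 and 0.77 at 0.7. The documents do not give r.

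**5. Why the 90% cannot simply be carried over.** As an illustration only, suppose the interaction effect were 0.18, every measurement had SD 0.20, and all four measurements had common correlation ρ. The SD of the interaction contrast is then 0.40√(1 − ρ).

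| ρ | SD of contrast | Power, n = 14 | Power, n = 20 |
|---|---|---|---|
| 0.3 | 0.335 | 46% | 63% |
| 0.5 | 0.283 | 60% | 77% |
| 0.7 | 0.219 | 81% | 94% |
| 0.9 | 0.126 | 99.8% | over 99% |

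The true power could lie on either side of 90%, and the documents do not say which.

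**The case against.** The mismatch itself is hard to dispute. Section 10 mentions reaching people through university students, but eligibility is 65 or over throughout, so that is a recruitment channel and not a young group. The serious objections concern weight and remedy.

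- **Proof of concept with a ceiling.** Such a study need not have 90% power, and nothing here shows that it is too small. That stands. But the plan states 90% and tests at 0.05, so the figure should describe those tests.
- **The basis is visible.** Section 6 openly names age differences and older and young adults, so a careful reader will see it. True, but that reader still finds no power for any planned test.
- **The replacement figures are generic.** They hold for any paired test of this size. That is fair: without an SD of change they say nothing in units of sway, step width variability or targeting accuracy. This is why the fix also asks for those SDs.
- **Which tests are covered.** The pre-post change within the perturbation session belongs to the synopsis analysis and is not listed in Section 6.1, whose time effect averages both sessions. That is correct. The contrast still serves the primary objective in Section 2.1, and the interaction serves the secondary one in Section 2.2. Section 6.1's time and session main effects are also 1-df contrasts, so the same formula applies with their own SDs.
- **Alpha for the interaction.** Section 6.1 sets 0.05 for each main effect and does not mention the interaction. Using 0.05 there is an assumption and should be labelled as one.
- **Sidedness is a side issue.** It depends on how the SDs are pooled and disappears if the figure is deleted. Agreed.

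**Conclusion.** The concern holds. The 90% with 14 per group describes a two-group age comparison and is not the power of any planned test. No other part of the document supplies that power, and none can be computed, because no expected change, SD of change or correlation is given.

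What the design alone supports is a detectable difference of 0.94 SDs (14 completers) to 0.76 SDs (20 completers) at 90% power, or 0.81 to 0.66 at 80%. These figures assume a two-sided 0.05 test, the interaction included, and a Pre-versus-Post contrast with 1 df. The synopsis does not state how many time levels its ANOVA has, and two secondary outcomes refer to 10 minutes of walking. An omnibus test on more than two levels would have different figures.

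The finding is about the justification of the sample size. It is not evidence that the trial is underpowered. It should be corrected, but it does not affect enrolment or conduct.

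**What to change.** Replace the Section 6 power statement with text such as:

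> With 14 (20) completers, a two-sided 0.05 test of a single within-subject contrast has 90% power for a mean difference of 0.94 (0.76) SDs of that difference, and 80% power for 0.81 (0.66). This applies to the pre-post change in the perturbation session and to the between-session difference in pre-post change (the time-by-session interaction, for which alpha 0.05 is assumed), each scaled by its own SD. The figures are for Pre versus Post (1 df) contrasts.

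Then:

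1. For postural sway, step width variability and foot placement targeting accuracy, add the SD of change and the detectable change in outcome units from the investigators' own data, or say that no estimate exists.
2. Drop the reference to groups.
3. Delete the older-versus-young figure. Otherwise label it as background and have the sponsor state its sidedness and whether ± means SD.

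The cost is one paragraph, plus the SDs of change if the investigators have them. No subjects are added, the design is unchanged, and the text does not require a choice between the synopsis ANOVA and the Section 6.1 ANOVA.

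### On the plan's own inputs, 14 per group gives about 83% two-sided power for the older-versus-young comparison; the stated 90% matches an undeclared one-sided test

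*Combined protocol and SAP*

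**What the plan says.** Section 6 holds the only sample-size justification in the document. It rests on published age-group differences and claims that "n=14 subjects per group would have 90% power to detect" a difference in dynamic instability during visually perturbed walking. The inputs are "healthy older (1.38 ± 0.20 , unitless) and healthy young (1.20 ± 0.10 , unitless) adults". Significance enters only as p<0.05: the sentence names no test, does not say whether it is one- or two-sided, and does not say what the ± values are. A second pair of inputs, for step width variability (8.92 ± 1.00 versus 4.02 ± 0.96), is said to be sufficiently powered by the same number.

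Section 6.1 plans a two-way repeated-measures ANOVA of time (pre, post) by session (perturbed, normal walking) and adds: "Significance will be defined for each main effect using an alpha level of 0.05". The synopsis plans a one-way repeated-measures ANOVA at the same alpha. Neither place mentions a directional hypothesis. On enrolment, Section 3.2 says: "We will recruit up to 20 older adults to participate".

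**The concern.** A power statement at p<0.05 for detecting a difference, with no direction given, is normally read as two-sided. The planned ANOVA F-tests are non-directional as well. If 90% is reached only by putting the whole 5% in one tail, the sentence claims more than its inputs deliver under the convention used in the rest of the plan.

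What is at stake is the accuracy of the one quantitative argument for the sample size, and what happens when it is revised. If the sponsor replaces the comparison but keeps an unstated one-sided convention, the new calculation will again be too optimistic for a two-sided F-test.

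**Working it through.** **Inputs, all from Section 6.** Older mean 1.38, SD 0.20; young mean 1.20, SD 0.10; 14 in each of two groups; alpha 0.05. Reading ± as SD is an assumption, because the plan does not label it.

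**Effect size.**
- Difference: 1.38 − 1.20 = 0.18
- Pooled SD: √[(0.20² + 0.10²)/2] = √0.025 = 0.158
- d = 0.18/0.158 = 1.138
- Noncentrality: d × √(n/2) = 1.138 × √7 = 3.012, with 2 × 14 − 2 = 26 df

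**Reproducing the stated 90%.** One-sided, the critical t on 26 df is 1.706. Power is P(T > 1.706) for a noncentral t with noncentrality 3.012, which is 90.1%. Thirteen per group gives 88.0%, so 14 is the smallest number that reaches 90% one-sided.

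**The same inputs, two-sided.** The critical value becomes 2.056, and power falls to 82.6%.

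| Method, n = 14 per group | One-sided 0.05 | Two-sided 0.05 |
|---|---|---|
| Equal-variance t (noncentral t) | 90.1% | 82.6% |
| Same test, 200,000 simulated trials | 90.0% | 82.5% |
| Unequal-variance (Welch) t, about 19 df | 89.6% | 81.5% |
| Normal approximation | 91.4% | 85.4% |

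Two-sided t-test power at other sizes is 89.6% for 17 per group, 91.3% for 18 and 93.9% for 20.

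**Can rounding explain the gap?** Pushing all four inputs to their rounding limits gives a two-sided t-test range of 75.8% to 88.4%. The upper end uses a difference of 1.385 − 1.195 = 0.19 with SDs of 0.195 and 0.095. The normal approximation at that same extreme corner gives 90.6%. So a two-sided 90% can be reached only by combining four favourable rounding errors with a large-sample formula at 14 per group.

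**Can a different pooling explain it?** Averaging the SDs arithmetically gives (0.20 + 0.10)/2 = 0.15. Two-sided power is then 86.3% by t-test and 88.8% by normal approximation. With that SD the normal approximation needs 15 per group for 90%, not 14.

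**Step width variability.** The difference is 8.92 − 4.02 = 4.90 and the pooled SD is √[(1.00² + 0.96²)/2] = 0.980, so d is about 5.0. Power is essentially 100% with either number of sides, so that sentence is unaffected.

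**Link to the planned analysis.** Each factor in Section 6.1 has two levels, so each F-test has one numerator degree of freedom and is equivalent to a two-sided t-test. The planned tests are two-sided at 0.05 unless the plan says otherwise, and it does not.

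**The case against.** The strongest objection is that the figure concerns a comparison the trial will not make. Only adults aged 65 and over are enrolled, there is no young group, and the analysis is within-subject. On that view the defect is the choice of comparison, and correcting 90% to 83% polishes an irrelevant number. Much of this stands, and it rules out several stronger readings:

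- A reader might infer that the trial carries a 17% rather than a 10% risk of a false negative, or that it is underpowered. The documents do not support this. They give no within-subject change, SD or correlation, so the power of the time-by-session test cannot be computed and could lie on either side of 83%.
- A reader might infer that 18 per group is needed. That number belongs to a two-group design and has no counterpart in one cohort of up to 20.
- A reader might infer that the authors chose a one-sided test. The plan does not say so. One-sided testing is the best-fitting explanation, because 14 is exactly the smallest number reaching 90% that way, but it remains an inference. The two-sided normal approximation with averaged SDs comes within about a point of 90%.

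A further objection is that the gap is small for a proof-of-concept study and changes no procedure. That is fair on impact. It does not make the sentence correct, and the sentence is the plan's only justification of sample size.

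**Conclusion.** The point holds in a limited form. On the plan's own inputs, 14 per group gives about 83% two-sided power (82.6% equal-variance, 81.5% Welch) for the older-versus-young difference in dynamic instability, against a stated 90%. The overstatement is 90 − 82.6 = 7.4 percentage points, or 8.5 with the Welch test. It rests on reading the ± values as SDs, on a t-test with standard pooling, and on taking p<0.05 as two-sided, in line with the non-directional F-tests of Section 6.1. No two-sided t-test variant tried reaches 90%.

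The error lies in a stated design property and is cheap to correct. It does not show that the trial is too small: neither 90% nor 83% is the power of any test that the trial will run.

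**What to change.** In Section 6:

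1. State that alpha is 0.05 two-sided, name the test, and say that the ± values are SDs, if they are.
2. Correct the figure to about 83% for 14 per group. Label it explicitly as the older-versus-young between-group comparison from earlier work and not as the power of this trial. Without that label the corrected number could mislead as much as the present one.
3. State that power for the within-subject time-by-session contrast, in a single cohort of up to 20, is a separate quantity. Give it two-sided, with the assumed within-subject change and the SD of that change. The documents supply neither, so the sponsor must provide them, ideally as a range.

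Items 1 and 2 cost one rewritten sentence and a less favourable stated figure, with no extra subjects and no change in procedure. Item 3 needs a short new calculation and the assumptions behind it.
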